5.5.3 Labelling

Labels will be prepared in accordance with Good Manufacturing Practice (GMP) and local regulatory guidelines. The labels will fulfill GMP Annex 13 requirements for labelling. Label text will be translated into local language, where appropriate.

5.5.4 Storage

All study drugs will be kept in a secure place under appropriate storage conditions. The IP label on the bottle specifies the appropriate storage. All study medications shall be stored in their original containers. Only staff members who are authorized to dispense the drug supplies will have access to them.

5.6 Concomitant and post-study treatment(s)

Concomitant medications allowed and their relation to stable medical conditions are outlined for control subjects with normal renal function in exclusion criteria [24](#) and for subjects with renal insufficiency in exclusion criteria [25](#).

No subjects should receive any new chemical entities or other clinical study IP within 1 month of TC-5214 administration.

Medication, which is considered necessary for the subject's safety and well being, may be given at the discretion of the Investigator during the residential period. When any medication is required, it should be prescribed by the Investigator who should inform the AstraZeneca CPA Physician. Following consultation with the CPA Physician, the Investigator should determine whether or not the subject should continue in the study.

Other medication, which is considered necessary for the subject's safety and well being, may be given at the discretion of the Investigator and recorded on the paper case report form (CRF).

5.7 Treatment compliance

The administration of all study drugs (including IP) should be recorded in the appropriate sections of the CRF.

Treatment compliance will be assured by supervised administration of the IP by the Investigator or representative. The dose, date, and time of administration of the IP will be recorded and checked by the monitor at monitoring visits.

5.7.1 Accountability

The study drug provided for this study will be used only as directed in the study protocol.

The study personnel will account for all study drugs dispensed to and returned from the subject, and return all unused drugs to AstraZeneca for destruction. Certificates of delivery and return should be signed by the appropriate personnel.

5.8 Discontinuation of investigational product

Subjects may be discontinued from IP in the following situations:

- Subject decision. The subject is at any time free to discontinue treatment, without prejudice to further treatment
- Risk to healthy subjects as judged by the Investigator or AstraZeneca
- Severe non-compliance to protocol as judged by the Investigator and/or AstraZeneca
- Incorrectly enrolled subject, the subject does not meet the required inclusion/exclusion criteria for the study
- Subject loss to follow-up
- If any AE, laboratory, vital sign or ECG changes are seen during or after dosing which would indicate that any further dosing may harm the safety of the subject, dosing must be stopped or further study treatment must be discontinued
- Positive pregnancy test for a female subject

5.8.1 Procedures for discontinuation of a subject from investigational product

A subject that decides to discontinue IP will always be asked about the reason(s) and the presence of any AEs. If possible, they will be seen and assessed by an Investigator(s). Adverse events will be followed up (see Sections 6.3.3 and 6.3.4).

If a subject is withdrawn from study, see Section 5.9.

5.9 Withdrawal from study

Subjects are at any time free to withdraw from study (IP and assessments), without prejudice to further treatment (withdrawal of consent). Such subjects will always be asked about the reason(s) and the presence of any AEs. If possible, they will be seen and assessed by an Investigator. Adverse events will be followed up (see Sections 6.3.3 and 6.3.4).

Subjects who are discontinued from IP or withdrawn from the study may be replaced as described in Section 5.2.

6. COLLECTION OF STUDY VARIABLES

The study assessments are described in the sections below and the timing of these assessments are detailed in the study plans ([Table 1](#) and [Table 2](#)).

It is important that PK sampling occurs as close as possible to scheduled time. In order to achieve this, other assessments scheduled at the same time may be initiated prior to the timepoint. The sequence at a particular time point is:

1. ECGs
2. Blood pressure (BP) and pulse rate
3. PK blood sample (Note: PK sampling must be performed at the precise protocol scheduled time.)
4. Urine collections
5. In Group 5 (Part 1, Period 2), dialysis related procedures will follow PK blood sample collections, where appropriate.

Pre-dose assessments may be performed up to 60 minutes prior to dosing.

6.1 Recording of data

The Investigator will ensure that all data collected in the study are recorded as specified by the protocol.

He/she ensures the accuracy, completeness, legibility and timeliness of the data recorded in the appropriate sections of the paper case report form (pCRF) and according to any instructions provided. The Investigator will sign the CRF and a copy will be archived at the study site.

The Investigator will provide AstraZeneca with all data produced during the study from the scheduled study assessments.

Procedures for data editing, entry, and handling of the data query process will be described in the data management plan. See [Section 10](#).

6.2 Data collection and enrollment

At enrollment (Visit 1), each potential subject will provide informed consent prior to starting any study-specific procedures.

Demographic data and other characteristics will be recorded and will include date of birth, sex, race, alcohol consumption, smoking history, drug use history and CL_{CR}.

Each subject will undergo screening during the 30 days prior to admission to confirm eligibility. This will consist of:

1. Obtaining written informed consent prior to starting any study-specific procedures are performed;
2. A standard medical, medication, and surgical history with review of the inclusion and exclusion criteria with the subject;
3. A complete physical examination;
4. Height, weight, and calculation of BMI;
5. Recording a resting 12-lead paper ECG;
6. A blood sample for routine clinical chemistry, hematology, and screen for hepatitis B surface antigen and antibodies to HIV;
7. Vital signs – blood pressure, pulse, and oral temperature;
8. A serum pregnancy test (females of childbearing potential only);
9. A midstream urine sample for routine urinalysis;
10. A drugs of abuse screen;
11. Collection of AEs;
12. Prior and concomitant medications;
13. Columbia Suicide Severity Rating Scale (C-SSRS).

The eGFR will be determined for each subject using the following abbreviated 4-variable MDRD equation ([National Kidney Foundation 2002](#)):

$$- \quad eGFR = 175 \times (\text{serum creatinine})^{-1.154} \times \text{age}^{-0.203} \times (1.210 \text{ if African American}) \\ \times (0.742 \text{ if female})$$

An online calculator from a reputable source (eg nephron.org) will be used to ensure a consistent calculation across subjects. After admission and before IP administration the Investigator should reassess each subject to reconfirm eligibility. The renal function determination at screening will be used to classify the subject to the renal function Groups 1 through 4; however, the eGFR value determined at check-in on Day -1 or Day -2 will be used for purposes of any statistical correlation of PK data with renal function.

6.2.1 Follow-up procedures

A poststudy medical examination will be performed 7 to 10 days after the final discharge from the study site. This will be similar to the one performed at screening and will include a complete physical examination, vital signs, recording a 12-lead paper ECG, a blood sample for clinical chemistry, hematology, a urine sample for urinalysis, CSSRS, and assessment of any AEs or required medication.

6.3 Safety

The Investigator is responsible for ensuring all staff involved in the study is familiar with the content of this section.

6.3.1 Definition of adverse events

An AE is the development of an undesirable medical condition or the deterioration of a pre-existing medical condition following or during exposure to a pharmaceutical product, whether or not considered causally related to the product. An undesirable medical condition can be symptoms (eg, nausea, chest pain), signs (eg, tachycardia, enlarged liver) or the abnormal results of an investigation (eg, laboratory findings, ECG). In clinical studies, an AE can include an undesirable medical condition occurring at any time, including run-in or washout periods, even if no study treatment has been administered.

The term AE is used to include both serious and non-serious AEs.

6.3.2 Definitions of serious adverse event

A SAE is an AE occurring during any study phase (ie, run-in, treatment, washout, follow-up), that fulfills one or more of the following criteria:

- Results in death;
- Is immediately life-threatening;
- Requires in-patient hospitalization or prolongation of existing hospitalization;
- Results in persistent or significant disability or incapacity;
- Is a congenital abnormality or birth defect; or
- Is an important medical event that may jeopardize the subject or may require medical intervention to prevent one of the outcomes listed above.

For further guidance on the definition of a SAE, see [Appendix B](#) to the Clinical Study Protocol.

6.3.3 Recording of adverse events

Time period for collection of adverse events

Adverse events will be collected from the time of signature of informed consent throughout the treatment period and including the follow-up period.

Follow-up of unresolved adverse events

Any AEs that are unresolved at the subject's last visit in the study are followed up by the Investigator for as long as medically indicated. AstraZeneca retains the right to request additional information for any subject with ongoing AE(s)/SAE(s) at the end of the study, if judged necessary.

Variables

The following variables will be collected for each AE;

- AE (verbatim);
- The date and time when the AE started and stopped;
- Maximum intensity on a scale of 1 to 3 (if the intensity of an AE changes, only the maximum intensity of the event will be recorded):
 - Mild (awareness of sign or symptom, but easily tolerated);
 - Moderate (discomfort sufficient to cause interference with normal activities); or
 - Severe (incapacitating, with inability to perform normal activities).
- Whether the AE is serious or not;
- Investigator causality rating against the IP (yes or no);
- Action taken with regard to IP;
- AE caused subject's withdrawal from study (yes or no);
- Outcome.

In addition, the following variables will be collected for SAEs:

- Date AE met criteria for SAE
- Date Investigator became aware of SAE
- AE is serious due to

- Date of hospitalization
- Date of discharge
- Probable cause of death
- Date of death
- Autopsy performed
- Causality assessment in relation to study procedure(s)
- Causality assessment in relation to other medication
- Causality assessment in relation to additional Study Drug
- Description of AE.

It is important to distinguish between serious and severe AEs. Severity is a measure of intensity whereas seriousness is defined by the criteria in Section 6.3.2. An AE of severe intensity need not necessarily be considered serious. For example, nausea that persists for several hours may be considered severe nausea, but not an SAE. On the other hand, a stroke that results in only a limited degree of disability may be considered a mild stroke but would be an SAE.

Causality collection

The Investigator will assess causal relationship between IP and each AE, and answer ‘yes’ or ‘no’ to the question ‘Do you consider that there is a reasonable possibility that the event may have been caused by the investigational product?’

For SAEs causal relationship will also be assessed for other medication and study procedures. Note, for SAEs that could be associated with any study procedure the causal relationship is implied as ‘yes’.

A guide to the interpretation of the causality question is found in [Appendix B](#) to the Clinical Study Protocol.

Adverse events based on signs and symptoms

All AEs spontaneously reported by the subject or reported in response to the open question from the study personnel: “Have you had any health problems since the previous visit/you were last asked?”, or revealed by observation will be collected and recorded in the CRF. When collecting AEs, the recording of diagnoses is preferred (when possible) to recording a list of signs and symptoms. However, if a diagnosis is known and there are other signs or symptoms that are not generally part of the diagnosis, the diagnosis and each sign or symptom will be recorded separately.

Adverse events based on examinations and tests

The results from protocol mandated laboratory tests and vital signs will be summarized in the clinical study report (CSR). Deterioration as compared to baseline in protocol-mandated laboratory values, vital signs, ECGs, and other safety assessments should therefore only be reported as AEs if they fulfill any of the SAE criteria or are the reason for discontinuation of treatment with the IP or if the Investigator insists on reporting them as an AE.

If deterioration in a laboratory value/vital sign is associated with clinical signs and symptoms, the sign or symptom will be reported as an AE and the associated laboratory result/vital sign will be considered as additional information. Wherever possible the reporting Investigator uses the clinical, rather than the laboratory term (eg, anaemia versus low hemoglobin value). In the absence of clinical signs or symptoms, clinically relevant deteriorations in non-mandated parameters should be reported as AE(s).

Deterioration of a laboratory value, which is unequivocally due to disease progression, should not be reported as an AE/SAE.

Any new or aggravated clinically relevant abnormal medical finding at a physical examination as compared with the baseline assessment will be reported as an AE.

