11. EVALUATION AND CALCULATION OF VARIABLES BY [REDACTED]

11.1 Calculation or derivation of safety variable(s)

All AEs will be collected for each subject from the time when informed consent is obtained (Visit 1) until the follow-up visit (Visit 3). AEs that occur before dosing will be reported separately.

Change-from-baseline variables will be calculated by [REDACTED] Inc for the safety variables listed below, as the posttreatment value minus the value at baseline. The baseline values will be as follows:

- Clinical laboratory tests: Day -1 value
- Vital signs (including supine blood pressure and pulse): Day -1 time-matched values
- ECG: Day 1

Baseline values for safety variables during each respective period will serve as the baseline value for that period.

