12.2.2 Safety

All safety data (scheduled and unscheduled) will be presented in the data listings.

Safety variables (ie, clinical laboratory values, vital signs, and ECGs) will be reported to the same precision as the source data. Derived variables will be reported using similar precision to those from which they were derived (eg, QT_c derived from QT interval).

Extra measurements (such as unscheduled or repeat assessments) will not be included in the descriptive statistics, but will be included in data listings. All AEs, ECG outliers, and clinical laboratory outliers that occur following the first dose of study medication will be included in the tabulations of AEs and outlier events, including episodes that occur at unscheduled evaluations.

All available data from subjects in the safety analysis set will be included in the safety analyses. No adjustment or imputation will be utilized for missing values or for subjects who withdraw prior to completing the study, neither will analyses be restricted to subjects with complete data.

All AEs will be collected for each subject when informed consent is obtained (Visit 1) until the follow-up visit (Visit 3). AEs that occur before dosing will be reported separately.

AEs will be summarized by preferred term and system organ class using MedDRA vocabulary (version 12.0 or higher) by treatment and across all treatments. Furthermore, listings of SAEs and AEs that led to withdrawal will be made and the number of subjects who had any AEs, SAEs, AEs that led to withdrawal, and AEs with severe intensity will be summarized.

Tabulations and listings of data for vital signs, clinical laboratory tests, ECGs, and physical examination findings will be presented. All continuous safety data will be summarized across all treatments for the absolute value at each scheduled assessment and for the corresponding change from baseline. For clinical laboratory tests, listings of values for each subject will be presented with abnormal or out-of-range values flagged. Clinical laboratory data will be reported in Système International units in the CSR.

For ECG parameters, the QT correction factor will be based on the Fridericia's formula. Further categorical summaries of absolute QT and QTcF values (greater than 450 ms, greater than 480 ms, greater than 500 ms) and change-from-baseline values in QT and QTcF values (greater than 30 ms, greater than 60 ms) may also be produced.

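### A non-serious adverse event that begins before dosing and worsens afterwards can be left out of the post-dose tables, because the date of worsening is not captured and no rule says where the event is counted

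*Supplement*

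**What the plan says.** Five statements in the revised protocol bear on this.

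- **Collection window, Section 6.3.3:** "Adverse events will be collected from the time of signature of informed consent throughout the treatment period and including the follow-up period". Symptoms during screening (up to 30 days), or on the day before dosing, are therefore AE records before any drug is given.
- **What is recorded, Section 6.3.3:** each AE has "The date and time when the AE started and stopped", together with seriousness, investigator causality, action taken, withdrawal and outcome. For intensity, "if the intensity of an AE changes, only the maximum intensity of the event will be recorded". Serious events also carry "Date AE met criteria for SAE".
- **Definition, Section 6.3.1:** an AE includes "the deterioration of a pre-existing medical condition following or during exposure to a pharmaceutical product".
- **Pre-dose events, Section 11.1 (repeated in 12.2.2):** "AEs that occur before dosing will be reported separately".
- **Post-dose events, Section 12.2.2:** events "that occur following the first dose of study medication will be included in the tabulations of AEs and outlier events".

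No section says where an AE is counted if it is ongoing at dosing and then gets worse.

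**The concern.** Comparing safety and tolerability between renally impaired and normal subjects is a secondary objective (Section 2.2). The post-dose AE tables are a main display for it. If a symptom such as dizziness or nausea is already an AE record when the subject is dosed, and then worsens, Section 6.3.3 can be read as keeping one record. That record has the pre-dose start and the post-dose maximum intensity. If the reporting rule is then applied by start time, the event goes to the separate pre-dose report. A possible drug effect is missing from the post-dose table, and its higher intensity appears against a pre-dose event.

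A definition of treatment-emergent events can properly be left to an analysis plan, and none is shown here. Data capture is different. If the CRF never asks when a non-serious AE worsened, no later analysis plan can supply the date.

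**Working it through.** The plan gives no figure to reproduce, so the check is to follow one event through the rules. Take a non-serious AE of mild intensity that starts after consent, is ongoing at dosing, and becomes moderate or severe afterwards.

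**Step 1: is it an AE record before dosing?** Yes. Collection starts at consent, and Section 6.3.1 allows an AE when no study treatment has been given.

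**Step 2: what does the record show after the worsening?** Two readings are open.

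- *Reading A, same event with a changed intensity (6.3.3).* There is one record, with a pre-dose start, a stop time and the maximum intensity. Nothing in it shows whether the maximum came before or after the dose.
- *Reading B, deterioration after exposure is itself an AE (6.3.1).* There is a second record with a post-dose start.

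The protocol does not choose between them. Section 6.3.3 speaks directly to changing intensity, so a site following it could reasonably adopt reading A. With up to 3 centers, practice could differ.

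**Step 3: where is it reported?** Under B it is tabulated post-dose. Under A it depends on what it means for an AE to occur before or after dosing. If the start decides, the event goes only to the separate pre-dose report and the listings.

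**Step 4: can the other recorded variables repair it?** The stop time shows that the event was ongoing at dosing, but not that it worsened. A causality rating of yes would flag it, but no rule moves a flagged event into the post-dose tables. The date on which SAE criteria were met covers only worsening to serious. The requirement in 6.3.3 to report aggravated findings is limited to physical examination. The gap is therefore confined to non-serious AEs.

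**Step 5: how large can it be?** Input: 8 subjects per group (Section 12.3).

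- One subject omitted from a group's AE count: 1/8 = 12.5 percentage points.
- Two subjects, purely as an illustration: 2/8 = 25 points.

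These are upper limits. Incidence of any AE falls only if the subject has no other post-dose AE. The count of subjects with a severe AE falls only if the subject has no other severe post-dose AE. The documents give no rate of pre-dose AEs, so the expected number affected cannot be computed.

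**The case against.** The strongest reply is that the plan already covers this case. Section 6.3.1 makes post-exposure deterioration an AE, so it can be entered with its own start and tabulated. The maximum-intensity rule can then be read as dealing with fluctuation within one event. In addition:

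- All safety data are listed, and a medical expert reviews non-serious AEs (Section 11.1.1).
- The named concern, orthostatic hypotension, is also followed through orthostatic blood pressure. It is measured before dosing, at 4 hours and each morning, and vital signs are analysed against time-matched Day -1 values. That analysis does not depend on AE onset.
- The affected set is narrow: the event must start after consent, be ongoing at dosing, and worsen without becoming serious.

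Most of this stands, and it is why the point is minor. It does not settle which reading sites should follow, and listings do not supply a date that was not collected.

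A reader might infer three stronger claims, none of which the documents support.

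- *Worsening events certainly drop out.* The reporting sections speak of events that occur, not events that start, and reading B keeps the worsening in the tables.
- *The loss falls mainly on dialysis subjects and biases the comparison toward no difference.* Dosing after dialysis makes pre-dose symptoms plausible in Group 5, but no figure shows how often they arise in any group. The direction is an assumption.
- *In Group 5 Part 1, an event that starts after the first dose and worsens after the second is lost.* The boundary in 12.2.2 is the first dose, so that event is already post-dose. Both periods use the same 2 mg dose (5.5.2) and data are presented by renal function group (12.2.1), so the renal-group comparison is unchanged.

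**Conclusion.** The concern holds as a minor one. For a non-serious AE with onset between consent and dosing, the protocol does not say whether post-dose worsening is a new record. It does not collect the date of the change and does not say in which table the event belongs. Such an event can be missing from the post-dose tables. The event itself is not lost, since it remains in the listings and the separate pre-dose report.

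The effect is at most 12.5 percentage points per affected subject in a group of 8. This assumes that the site keeps a single record, that the start time decides the table, and that the subject has no other qualifying post-dose AE. How many subjects would be affected, and in which groups, is unknown. Safety is summarised descriptively, so no formal test is at risk.

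**What to change.** In Section 6.3.3, state that an AE ongoing at dosing that increases in intensity after dosing is entered as a new AE with onset at the time of worsening. Collecting the date and time of the intensity change on the existing record would serve equally well. In Section 12.2.2, define post-dose AEs as those that start or worsen after dosing. This brings the recording rule into line with the definition in 6.3.1.

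The cost is a CRF completion instruction (or one added field), a sentence in each of the two sections, and a few extra AE records. Counts of events may rise slightly because one symptom can produce two records. Counts of subjects with an AE, which 12.2.2 also summarises, are not inflated by the split.

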For Groups 1 through 3 the duration of each subject's participation will be approximately 47 days, including a screening period of up to 30 days, a treatment period consisting of 6 to 7 nights (depending on the admission day) and a follow-up visit, 7 to 10 days after discharge from the treatment period.

For the first 4 subjects in Group 5 (Part 1) participating in the 2-period portion of the study, duration of each subject's participation will be approximately 55 days. These subjects will be given the option to remain at the clinic between samplings for the off dialysis assessment (post dialysis dosing) at the discretion of the Investigator.

For the remaining subjects in Group 5 (Part 2) participating in a single treatment period, duration of each subject's participation will be approximately 47 days.

Subjects may be admitted to the clinic on Day -2 for the Day -1 assessments at the discretion of the Investigator.

Outcome variable(s):

- Pharmacokinetic
 - Primary plasma pharmacokinetic parameters: AUC and C_{max},
 - Secondary plasma pharmacokinetic parameters: CL/F, t_{1/2}, t_{max}, and V_z/F in all subjects; Ae, CL_D, and fe in Groups 1 to 4; A_{d(4-8)}, Cl_R, and fd₍₄₋₈₎ in Group 5 during Period 2

- **Safety**

Adverse events and serious adverse events including severity, vital signs, physical examinations, laboratory parameters, electrocardiograms, and the Columbia-Suicide Severity Rating Scale.

Statistical methods

Tabulations and listings of data for vital signs, physical examinations, clinical laboratory tests, and electrocardiograms will be presented. Results from the Columbia Suicide Severity Rating Scale will be presented separately in a listing only. For clinical laboratory tests, listings of values for each subject will be presented with abnormal or out-of-range values flagged (other than those associated with renal impairment and /or stable chronic condition). Plasma and urine concentration data and the derived pharmacokinetic parameters will be summarized by renal function group using descriptive statistics.

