6.3.8 Other safety assessments

6.3.8.1 Columbia Suicide Severity Rating Scale

The C-SSRS (see [Appendix D](#)) will be administered to all volunteers as outlined in the study plans [Table 1](#) and [Table 2](#). The C-SSRS is a low burden, clinician administered tool designed to track suicidal AEs throughout any treatment trial and is considered to be the “gold standard” for assessment ([Posner K 2007](#)). The measure succinctly covers the full spectrum of suicidality addressing both behavior and ideation and is now required by the US Food and Drug Administration (FDA) in clinical trials.

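### By default, non-serious worsening found only on the C-SSRS is not recorded as an AE, and the reason given for that rule does not apply to the scale

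*Supplement*

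**What the plan says.** Section 6.3.3, in its part on examinations and tests, first promises a summary of mandated laboratory and vital-sign results in the study report. It then draws a consequence, saying of worsening against baseline in mandated laboratory values, "vital signs, ECGs, and other safety assessments should therefore only be reported as AEs if they fulfill any of the SAE criteria", and continuing "or are the reason for discontinuation of treatment with the IP or if the Investigator insists on reporting them as an AE". There are thus three routes to an AE.

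The protocol has a section headed "6.3.8 Other safety assessments". Its single entry is the C-SSRS (6.3.8.1), described there as a "clinician administered tool designed to track suicidal AEs throughout any treatment trial". The synopsis names the scale among the safety outcome variables. Tables 1 and 2 schedule it at screening, on Day -1, on the discharge day and at follow-up.

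On reporting, the synopsis states: "Results from the Columbia Suicide Severity Rating Scale will be presented separately in a listing only". Section 12.2.2 says: "Tabulations and listings of data for vital signs, clinical laboratory tests, ECGs, and physical examination findings will be presented". It does not mention the C-SSRS.

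**The concern.** The restriction makes sense for data that are tabulated anyway: a shift in a laboratory value need not be an AE because the reader sees it in the laboratory summary. The C-SSRS falls under the same restriction but has no summary. A new, non-serious positive answer on the scale after dosing may therefore go unrecorded as an AE and also appear in no table.

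Two things are at stake. Intensity, causality, outcome and follow-up of unresolved events are collected under Section 6.3.3 for AEs, and a line in a C-SSRS listing does not trigger them. In addition, the AE incidence by renal function group could understate psychiatric findings for a drug with central nervous system activity (Section 1.1), in a study that excludes subjects judged at risk of suicide (Section 4.2, criterion 2).

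**Working it through.** The plan gives no figure to reproduce on this point. The check sets the sections against each other, followed by two lines of arithmetic.

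**1. Does the rule reach the C-SSRS?** The rule in 6.3.3 names four kinds of mandated data: laboratory values, vital signs, ECGs and other safety assessments. The last term is the title of Section 6.3.8, which contains only the C-SSRS. Yes.

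**2. Does the reason for the rule hold?** The preceding sentence in 6.3.3 refers to laboratory tests and vital signs. Section 12.2.2 tabulates both, and ECGs as well. So three of the four kinds of data have a table. The fourth, the C-SSRS, has a listing only.

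**3. Do neighboring provisions cover it?**
- The sentence in 6.3.3 on worsening accompanied by clinical signs or symptoms concerns laboratory values and vital signs.
- The sentence on worsening without symptoms concerns non-mandated parameters; the C-SSRS is mandated.
- Physical examination findings have their own sentence making new or aggravated clinically relevant findings AEs. The C-SSRS has none.
- Beyond the AE list itself, the expert review for other significant AEs (11.1.1) covers laboratory, vital-sign and ECG data.

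**4. How far do the three routes reach?**
- *Seriousness:* Section 6.3.2 includes important medical events, so some ideation or behavior could qualify. Non-serious worsening by definition does not.
- *Discontinuation of IP:* under Section 5.5.2 only Group 5, Part 1 is dosed twice. The synopsis plans about 32 subjects, 4 of them in that subgroup: 32 − 4 = 28 with no IP left to discontinue after dosing. For the other 4 this route closes after the second dose.
- *Investigator insists:* open for every subject with no seriousness condition, but discretionary, at up to 3 centers.

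**5. Is there a route outside this rule?** Yes. The signs-and-symptoms part of 6.3.3 collects AEs that are volunteered, given in answer to the open health question or revealed by observation, with no seriousness condition. Section 12.2.2 tabulates them. An answer to a scripted C-SSRS question is neither volunteered nor a reply to the open question. The protocol does not say whether it counts as observed, and the more specific rule on mandated assessments points the other way.

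**6. Illustrative size.** If one subject in a group of 8 had such a finding and no route were used, the true proportion would be 1/8 = 12.5% and the AE table would show 0/8 = 0%. This is a hypothetical case; the documents give no expected rate.

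**The case against.** A reader might infer that the rule bars all non-serious suicidal ideation from being an AE and that it then disappears from the report. The documents do not support that. The sentence has two exceptions besides seriousness, and the investigator's applies to everyone. The symptom route is separate and unconditional. Ideation with intent or a plan, or suicidal behavior, might meet the important-medical-event criterion. The C-SSRS results are listed, and in an open-label study of about 32 subjects a positive entry would be easy to find. The scale is also repeated at follow-up. Nor does the rule stop the scale from being given or recorded; it limits only what becomes an AE by default.

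It can also be said that listing-only presentation is an openly stated choice in an exploratory study with 8 subjects per group. No separate analysis plan is shown, so the silence of Section 12.2.2 on C-SSRS tables is not a fault by itself.

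All of this stands, and it reduces the problem to non-serious worsening found only on the scale. It does not remove that problem. The default is written into the protocol, its reason does not fit this instrument, and it sits badly with the stated purpose of tracking suicidal AEs. Sites are left to settle for themselves whether a scripted answer is a symptom or a test result.

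**Conclusion.** The point holds in a limited form and is minor. By default, non-serious C-SSRS worsening that does not also arise as a reported or observed symptom becomes an AE only if it leads to discontinuation of IP, which has little practical reach for 28 of about 32 planned subjects, or if the investigator insists. Otherwise it appears in a listing and could be absent from the AE tables.

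The conclusion rests on two readings: that the term in 6.3.3 means what the heading of 6.3.8 covers, and that an answer to a C-SSRS question is not automatically an observed sign or symptom. Were the sponsor to read such answers as observed symptoms, the AE gap would close in practice, but the text would still need to say so. The number of subjects actually affected cannot be estimated from the documents and may be zero.

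**What to change.** In Section 6.3.3, add a sentence exempting the C-SSRS from the restriction: ideation or behavior that is new or worse after dosing, relative to the Day -1 C-SSRS, is recorded as an AE. For the 4 two-period subjects, state which Day -1 assessment is meant; Section 11.1 uses each period's own baseline for other safety variables.

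In Section 12.2.2, add the number of subjects in each renal function group with such a finding, and keep the listing.

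The cost is one sentence and one small table. No assessment is added, because the scale is already scheduled on Day -1, at discharge and at follow-up. The downside is possibly a few extra non-serious AE reports.
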